**MEDICAL UNIVERSITY OF SOUTH CAROLINA**  
**Protocol****PI Names:** [name], M. D.**Study Title:** Effects of Cortical Dopamine Regulation on Drinking, Craving, and Cognitive Control**A. SPECIFIC AIMS, BACKGROUND AND SIGNIFICANCE****1) Alcohol use disorder, prefrontal dopamine, and catechol-O-methyltransferase**

Alcohol use disorder (AUD) is a devastating disease characterized by dysregulated motivation for alcohol and loss of control over consumption. In the brain, motivated behavior and cognitive control are mediated, in part, by dopamine (DA) signaling between the striatum and prefrontal cortex (PFC) (1). In humans, the PFC is a large and heterogeneous region with relatively high expression of both D1- and D2-like DA receptors. It comprises regions that underlie processing of learned reward values, including the orbitofrontal cortex (OFC) and ventromedial PFC (vmPFC) (2), as well as regions that underlie decision-making and inhibitory control, including the inferior frontal gyrus (IFG) (3) and dorsomedial and dorsolateral PFC (dmPFC and dlPFC) (4). These cortical areas interact in networks with striatal subregions to exert control over motivated behavior (5). The relationship between cortical DA and cognitive control has been hypothesized to be inverted-U-shaped (see **Figure 1**), with both high and low tone associated with poor control (6-8) (though other shapes for this relationship have also been proposed; 9). Thus, dysregulated inactivation of cortical DA, leading to excessive synaptic accumulation or removal, may contribute to loss of control in AUD and other addictive disorders.

Dysregulation of DA function in AUD has been studied for many years. Early human positron emission tomography (PET) studies found decreases in striatal D2 receptor availability (10) and DA transmission (11) among alcoholics, relative to controls, but were limited by the lack of DA radioligands that bound in PFC. Decreased striatal D2 availability was correlated with increased vmPFC response to alcohol cues (12), but direct ascertainment of cortical DA and its relationship to alcohol use was not possible. Recently, however, a PET study that used a novel cortical DA ligand, [11C]FLB 457, reported that prefrontal DA transmission was substantially down-regulated among recently abstinent alcoholics, particularly in the vmPFC, OFC, and dlPFC (13). These findings accord with recent animal data from the Charleston ARC, which suggest that chronic intermittent alcohol exposure profoundly disrupts the ability of D2-like receptors in the vmPFC to regulate pyramidal neuronal firing—independent of changes in receptor expression (14).

In most brain areas, including the striatum, DA is inactivated primarily through active reuptake at the presynaptic dopamine transporter (DAT). In the PFC, however, the DAT is not highly expressed (15), and the principal method of DA inactivation is degradation by the enzyme catechol-O-methyltransferase (COMT) (16). A single nucleotide polymorphism (SNP) in COMT, the gene that encodes this enzyme, has been associated with differential COMT function. Specifically, the met (A) allele of the val158met SNP (rs4680), which engenders a valine to methionine amino acid substitution, is associated with a three- to four-fold reduction in COMT efficacy (17), and thus greater synaptic DA accumulation, relative to the val allele, which is associated with low PFC DA tone (see **Figure 1**).

The val158met SNP is among the most thoroughly studied genetic variants in psychiatry (18; 19). Although initial studies showed an association with cognitive function, subsequent meta-analyses found no effect on this phenotype (20). Associations with alcohol-related phenotypes have also been mixed (21-24). More recent studies suggest, however, that COMT val158met variation may moderate response to DAergic medications, including olanzapine (25), methylphenidate (26), haloperidol (27), the D2 antagonist sulpiride (28), and the COMT inhibitor tolcapone (29-32) and entacapone (33). Given the evidence of dysregulation of DA function among individuals with AUD, it seems likely that a DAergic medication might reduce drinking in this population, and that the val158met SNP might moderate this response.

[figure not shown]

**Figure 1.** Conceptual diagram of the relationship between PFC DA tone and cognitive control, and the effects of *COMT* val158met variation on DA tone in this region. Our preliminary data suggest that **aripiprazole**, a DA partial agonist that we have tested in the current ARC funding period, may shift met-allele homozygotes into the optimal DA zone for control over drinking. Conversely, **tolcapone**, a COMT inhibitor and novel medication for AUD that we propose to test here, may shift val-allele homozygotes into this zone.

## B. Aripiprazole preliminary data and progress report

[figure not shown]
During the current ARC funding period, we tested this pharmacogenetic hypothesis by evaluating the interactive effects of *COMT* val158met variation and aripiprazole (APZ), a D2 partial agonist that is believed to stabilize cortical and striatal DA transmission, possibly by reducing both when they are upregulated (34) (although it also has serotonergic effects). We administered APZ to non-treatment-seeking subjects with early-stage alcohol dependence (i.e., individuals ages 21-40). To date, 60 subjects (mean age = 27, 75% male, average of 9 drinks/drinking day) have completed the study, in which they were randomized to APZ (titrated to 15 mg daily) or placebo for eight days, and completed alcohol cue-reactivity and stop-signal ( $N = 23$ ) fMRI tasks on day 7 and an alcohol self-administration paradigm (bar lab) on day 8. We used the cue-reactivity and stop-signal tasks because they assess motivated behavior and cognitive control and because PET studies suggest that these tasks strongly elicit cortical and striatal DA release (35; 36). We assessed the effects of APZ and *COMT* variation on the number of drinks, out of eight possible, that subjects chose to consume in the bar lab and on brain activation elicited by alcohol cues, as well as activation related to response inhibition.

Our preliminary data indicate that APZ trended toward reducing both drinks per drinking day during the first six days on medication ( $F(1, 57) = 3.15, p = .08$ ) and drinking in the bar lab ( $F(1, 57) = 2.50, p = .12$ ). However, the effect of APZ on bar-lab drinking was driven almost entirely by an interaction between medication group and variation at the *COMT* val158met SNP ( $F(2, 53) = 3.35, p < .05$ ; see **Figure 2**). Met-allele homozygotes who received APZ chose to consume, on average, two drinks, while those who received placebo chose to consume over seven drinks. While preliminary, this finding could account for some of the mixed findings from previous clinical trials of APZ for alcohol dependence (e.g., 37): APZ might be effective primarily for “early stage” individuals who are homozygous for the *COMT* met allele. Importantly, covarying for APZ-related side effects (e.g., sedation) did not reduce the statistical significance of this finding.

[figure not shown]
**Figure 2.** Interaction between APZ and *COMT* val158met genotype on bar-lab drinking. APZ reduced drinking among met-allele homozygotes ( $F(1, 53) = 8.98, p = .004$ ), but was not significantly different from placebo for heterozygotes or val-allele homozygotes.

APZ and COMT val158met genotype also interacted in their effects on alcohol cue-elicited brain activation. A whole-brain analysis of this interaction identified a cluster in the right and medial OFC (Brodmann area [BA] 11) in which COMT genotype significantly moderated the effect of APZ on cue-elicited activation. APZ, relative to placebo, decreased cue-elicited OFC activation among met-allele homozygotes, but increased it among val homozygotes (see **Figure 3**). Further, OFC activation was positively associated with the number of drinks subjects consumed in the bar lab ( $r(60) = 0.26, p < .05$ ), and when it was added to the model that tested the interactive effects of APZ and COMT genotype on bar-lab drinking, the interaction was no longer significant ( $F(2, 52) = 2.00, p = .15$ ), suggesting that cue-elicited activation in this region mediated the effect.

**Figure 3.** Interaction between APZ and COMT val158met genotype on alcohol cue-elicited OFC activation. The color scale indicates voxels in which these factors moderated cue-elicited activation (thresholded, voxelwise, at  $z > 1.96$ ).

A subset ( $N = 23$ ) of the subjects in the current ARC study were also administered a response inhibition (stop-signal) fMRI task (38). For this task, activation to task trials on which subjects failed to inhibit a response was contrasted with activation to trials on which they successfully inhibited a response (i.e., unsuccessful vs. successful inhibitions). A whole-brain analysis indicated that, although APZ did not significantly affect activation associated with this contrast, COMT genotype did, such that, irrespective of medication, val-allele homozygotes, relative to heterozygotes and met homozygotes, displayed greater dmPFC (BA 9) activation during unsuccessful inhibition (see **Figure 4**). This finding is consistent with other reports that COMT val-allele carriers demonstrate dysregulated cortical activation indicative of compromised cognitive function (39). Activation of dmPFC did not mediate the interaction of APZ and COMT genotype on bar-lab drinking, but this conclusion is limited by the current sample size.

of COMT val158met genotype on dmPFC activation associated with unsuccessful response inhibition. The color scale indicates voxels in which COMT genotype significantly moderated the unsuccessful > successful contrast (thresholded, voxelwise, at  $z > 1.96$ )

Collectively, the current data suggest that a novel pharmacogenetic interaction between a DAergic medication (APZ) and COMT variation is mediated by changes in cue-elicited cortical activation, such that APZ appears to be more effective in reducing drinking and cue-elicited activation among met-allele homozygotes. Interestingly, while APZ's effect on drinking was not mediated by changes in brain activation related to cognitive control (or the lack thereof), val-allele homozygotes, relative to heterozygotes and met homozygotes, demonstrated greater cortical activation during failed response inhibition. Thus, these findings raise the question of whether a different

medication might be more effective in reducing drinking among *COMT* val homozygotes, who derived little drinking reduction from APZ, and whether such a medication might exert its effects through changes in a reward-related phenotype, such as cue reactivity, or through a control-related phenotype, such as response inhibition. Because the *COMT* val allele is associated with relatively lower cortical DA, one possibility is that a medication that increases cortical DA could “rescue” cognitive control and reduce drinking among *COMT* val-allele homozygotes.

### 3) Rationale for the *COMT* inhibitor tolcapone as a medication to treat AUD

As noted above, *COMT* is the primary mechanism for DA inactivation in the PFC; thus, medications that inhibit this enzyme could achieve the aim of increasing cortical DA. Tolcapone, a brain-penetrant, reversible *COMT* inhibitor (40) that is FDA-approved for the treatment of Parkinson’s disease (41), offers an opportunity to test this hypothesis. Tolcapone acutely increases DA concentrations in both the periphery and the PFC (42). Among Parkinson’s patients, it is normally co-administered with levodopa (L-DOPA) to reduce peripheral metabolism of the latter before it enters the brain. As described in greater detail below, there are issues with tolcapone’s hepatotoxicity that likely preclude extended use of this medication to reduce heavy drinking in the general clinical population. Thus, this proposal presents a sub-acute treatment study in which tolcapone is used as a pharmacogenetic proof-of-concept probe. Tolcapone’s efficacy in reducing drinking would suggest that *COMT* inhibition is a possible pharmacological target for AUD, and other brain-penetrant, non-hepatotoxic *COMT* inhibitors could be developed to achieve similar or enhanced therapeutic results.

Data from animal models support the idea that tolcapone might be effective in increasing cognitive control and reducing drinking. Tolcapone increased DA release in the PFC during executive functioning tasks (42; 43), and in an animal model of cue-elicited drinking, it was recently reported to reduce alcohol consumption among both alcohol-preferring (P) and high-drinking Wistar rats (44). When administered independently of L-DOPA, tolcapone appears to have relatively limited effects on striatal DA or motor function (45; 46), likely because the greater expression of DAT in the striatum, relative to *COMT*, counteracts its acute effects. This differential regional effect further raises the question of whether, among individuals with AUD, tolcapone’s effects on drinking might be mediated through changes in a reward-related mechanism, such as cue reactivity (as we have shown for APZ), or through a more cortically-dependent mechanism, such as cognitive control.

Human studies offer additional evidence that tolcapone enhances cognitive function, and suggest that this effect may be specific to individuals homozygous for the val (higher activity) allele of the *COMT* val158met SNP, who have lower cortical DA and thus fall on the left side of the inverted-U-shaped function discussed above (see Table 1). Among healthy controls, tolcapone, given either acutely or over an eight-day span, improved performance on executive functioning, working memory, and set-shifting tasks, as well as pre-pulse inhibition of the startle response, a phenomenon believed to reflect cognitive efficiency (29; 30; 32). In two of these studies, beneficial cognitive effects were largely specific to val-allele homozygotes (29; 30), and in the third, these effects were moderated by variation at another *COMT* SNP that also regulates *COMT* activity (32). Two more recent studies of healthy controls also reported the effects of tolcapone on cognitive tasks more relevant to addictive behavior. An acute dose of tolcapone (200 mg) decreased risky decision-making only among val-allele homozygotes, and also improved working memory performance among these individuals (31). Further, the same acute dose of tolcapone reduced impulsive choice on a delay-discounting task (47). Thus, among individuals with AUD, tolcapone might act to “rescue” impaired cognitive control over heavy drinking.

Several of the studies noted above also employed neuroimaging paradigms; collectively, they suggest that tolcapone's effects may be mediated through changes in cortical activation and the connectivity of corticostriatal networks. These studies have primarily reported tolcapone-mediated reductions in cortical activity during cognitive tasks, and have been interpreted as evidence of improved cortical efficiency, although not all effects have been consistent, and few studies have examined interactions with *COMT* genotype. Among healthy controls, tolcapone, relative to placebo, decreased dlPFC and dmPFC activation during working memory and attentional control (29; 50) and reduced corticostriatal connectivity during a delay-discounting task (47). Similarly, among smokers, tolcapone, relative to placebo, reduced dlPFC and dmPFC activation related to working memory; interestingly, this effect occurred only among *COMT* val-allele homozygotes (49). However, tolcapone also increased dlPFC and dmPFC activation during the delay-discounting task noted above, and among pathological gamblers treated with tolcapone, improvement in gambling urges was related to increased fronto-parietal activation, relative to a baseline scan, during an executive planning task (48). Overall, neuroimaging data suggest that tolcapone may improve cognition through alterations in cortical activation and corticostriatal network connectivity.

#### 4) Tolcapone preliminary data

Given our preliminary data with APZ and the literature reviewed above, we sought to evaluate the effects of tolcapone among non-treatment-seeking individuals with AUD. The MUSC Institutional Review Board for Human Research approved an open-label pilot safety and feasibility study with similar parameters to the study proposed here (i.e., same dosing schedule and bar-lab paradigm). To date, five non-treatment-seeking subjects with normal liver function have enrolled in the study, with no significant adverse events and minimal liver enzyme elevation observed in only one subject, who was discontinued from the study before the bar lab. Urinary riboflavin measurements indicate that all subjects have been adherent to the protocol. Subjects' drinking decreased from 80% heavy drinking days (i.e.,  $\geq 5/4$  drinks/day for men/women) during the 90 days prior to the study to 50% heavy drinking days while on medication (paired *t*-test:  $t(3) = 2.85, p = .065$ ); while very preliminary, this trend lends further support to the hypothesis that tolcapone will reduce drinking.

### B. RESEARCH DESIGN AND METHODS

#### 1) Timeline and general design of the study

Enrollment and data collection will be conducted during years 1-4 and the first half of year 5; the study blind will be broken in the second half of year 5, and data analysis will begin at that point. Ninety non-treatment-seeking subjects (20 per year in years 1-4, and 10 in year 5) with *DSM-5* Alcohol Use Disorder (AUD) will be randomized, on the basis of their *COMT* genotype, to tolcapone (titrated to 200 mg, 3x/day) or placebo for seven days, and will complete the procedures detailed in **Table 2**. Immediately prior to randomization (day 1), subjects will undergo a pre-treatment fMRI scan, during which anatomical, alcohol cue-reactivity, and stop-signal scans will be acquired. If more than one week has passed between a subject's initial assessment by the ARC Clinical

Intake and Assessment Core, urine drug screening and pregnancy testing will be repeated, as will measures of recent alcohol consumption (e.g., Timeline Follow-back and Obsessive Compulsive Drinking Scale). On study day 7, subjects' drinking over the previous six days will be assessed, and the fMRI procedures will be repeated. Blood will be drawn on days 1 and 7 to assess tolcapone effects on COMT activity in red blood cells. On day 8, subjects will be counseled regarding alcohol problems and encouraged to participate in treatment if indicated. Subjects will be compensated \$300.

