### Exclusion Criteria:

1. Current *DSM-5* diagnosis of any other substance use disorder except Nicotine Use Disorder.
2. Any psychoactive substance use (except marijuana and nicotine) within the last 30 days, as indicated by self-report and urine drug screen. For marijuana, no use within the last seven days by verbal report and negative (or decreasing) urine THC levels.
3. Current *DSM-5* Axis I diagnosis, including major depression, panic disorder, obsessive-compulsive disorder, post-traumatic stress disorder, bipolar affective disorder, schizophrenia, dissociative disorders, eating disorders, or any other psychotic or organic mental disorder.
4. Current suicidal ideation or homicidal ideation.
5. Need for maintenance or acute treatment with any psychoactive medication, including antiepileptic medications.
6. Currently taking medication known to affect alcohol intake (e.g., disulfiram, naltrexone, acamprosate, topiramate).
7. History of severe alcohol withdrawal (e.g., seizure, delirium tremens), as evidenced by self-report and assessment with Clinical Institute Withdrawal Assessment for Alcohol-Revised (CIWA-Ar).

8. Clinically significant medical problems such as cardiovascular, renal, gastrointestinal, or endocrine problems that would impair participation or limit medication ingestion.
9. Past alcohol-related medical illness, such as gastrointestinal bleeding, pancreatitis, or peptic ulcer.
10. Current or past hepatocellular disease, as indicated by verbal report or elevations of SGPT (ALT) or SGOT (AST) greater than the upper limit of the normal range at screening.
11. Females of childbearing potential who are pregnant (by urine HCG), nursing, or who are not using a reliable form of birth control.
12. Current charges pending for a violent crime (not including DUI-related offenses).
13. Lack of a stable living situation.
14. Presence of ferrous metal in the body, as evidenced by metal screening and self-report.
15. Severe claustrophobia or morbid obesity that preclude placement in the MRI scanner.
16. History of head injury with > 2 minutes of unconsciousness.

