Nonetheless, given past reports of liver toxicity, caution is in order and reduction of risk is required. Subjects in this study will take tolcapone for only seven days, a period shorter than the FDA's first recommended interval for LFTs (after two weeks of dosing). However, heavy-drinking subjects may be at increased risk for liver compromise. Therefore, only individuals who 1) report no history of past liver disease and 2) have normal liver enzymes prior to randomization will be enrolled in the study. In our current ARC study, 23% of subjects had elevated liver enzymes; thus, we do not anticipate that this exclusion criterion will unduly limit recruitment. Subjects will be contacted on day 4, after they have taken medication for three days, to inquire about their wellbeing, including any complaints of abdominal pain, gastrointestinal disturbance, extreme fatigue, or skin color change. If any liver-related complaints are present on day 4, subjects will be discontinued from further study. These symptoms will also be assessed in person on day 7, and LFTs will be repeated on day 7 or 8, after medication administration is complete; if liver-related complaints are present or liver enzymes are elevated at that time, we will continue to monitor until they return to normal, and/or consider a referral to a hepatologist. To date, we have used this procedure in ten individuals who completed a prior pilot study and over 70 who have been enrolled in the current protocol; it has worked well.

**b) Adherence.** Given that subjects will not be seeking treatment, adherence to medication ingestion could be of concern. To monitor adherence, study medication will be over-encapsulated with 25 mg of riboflavin (which, in our experience, yields urine levels 2-3x normal basal levels up to 24 hours after medication ingestion), and urinary riboflavin will be measured in the CNL. Urine will be collected twice at baseline (to obtain a more valid average daily output) and on day 7. A spectrofluorometric assay with known aqueous standards will be used to develop a standard fluorescence curve from which to read the fluorescence of urine samples. Riboflavin levels will be compared between medication and genotype groups; levels > 1500 ug/ml will be considered adherent. Although urinary riboflavin is not a perfect measurement of adherence,

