#### 4) Test procedures

**a) Pre-treatment scan session (day 1).** Upon their arrival at the MRI suite, subjects give a breath or saliva sample for alcohol testing, to ensure they have not recently consumed alcohol, and administered the Clinical Institute Withdrawal Assessment for Alcohol-Revised (CIWA-Ar; 65), to ensure they are not currently experiencing significant alcohol withdrawal symptoms. Subjects with a breath or saliva alcohol content  $> 0.02$  will be rescheduled, and those with a CIWA-Ar score  $> 3$  will not be scanned. However, in our experience, very few subjects arrive intoxicated or in alcohol withdrawal. Subjects will then be administered the Vocabulary and Matrix Reasoning subtests of the Wechsler Abbreviated Scale of Intelligence-II (WASI-II). For subjects who were referred from study 46264 (PI: [name]), the WASI-II score from that study will be used, since this assessment cannot be repeated over short intervals. Scans will be performed with a Siemens 3.0T TIM Trio MR scanner with actively shielded magnet and high-performance gradients (45 mT/m, 200 T/m-sec). Each scan will last approximately 60 minutes and will consist of a high-resolution anatomical image, for subsequent stereotactic registration, and two gradient-echo echoplanar imaging (EPI) sequences: 1) an alcohol cue-reactivity task; and 2) three runs of a response inhibition task. [name] will supervise all aspects of the proposed neuroimaging procedures, which are similar to those used in our current ARC project. Following the scan, blood will be collected for the red blood cell COMT activity assay. Subjects will then be randomized to tolcapone or placebo medication, and will take their first dose of medication at the study site.

[figure not shown]

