## C. PROTECTION OF HUMAN SUBJECTS

### 1) Risks to Human Subjects

#### a) Human Subjects Involvement, Characteristics, and Design

We anticipate that the ARC Clinical Intake and Assessment Core (CIAC) will refer 90 subjects to us for participation. Half of these subjects will be randomized to tolcapone, and the other half to placebo medication. We anticipate that 70% of subjects will be male and 30% female, and that approximately 20% of subjects will be racial and ethnic minorities. No special vulnerable populations will be involved in this research.

During assessment at the CIAC, subjects will receive liver function tests, and those with normal liver enzymes (transaminases) will be genotyped for the COMT val158met single nucleotide polymorphism (SNP). Due to the allele frequencies for this SNP, all subjects with the met/met genotype will be referred for participation, as will approximately half of the subjects with the val/met genotype and two-thirds of the subjects with the val/val genotype. Subjects with normal liver enzymes who have the val/met or val/val genotype will be randomly chosen for referral to this study or to the other clinical component of the ARC or an ARC pilot study.

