**b) Protections Against Risk**

1. To minimize risks to privacy of individuals and confidentiality of data, besides the study identification number assigned at the beginning of each subject's participation in the study, no other identifiers will be used. All research records will be stored in locked cabinets and only the faculty and staff listed on this grant application or their replacements will have access to those records. All laboratory tests will be coded only with a subject number to ensure confidentiality. To assure confidentiality of genetic samples, only the study identification number will be used.
2. To minimize the risk of serious alcohol withdrawal symptoms, potential subjects will be evaluated before inclusion in the study. Subjects with a Clinical Institute Withdrawal Assessment for Alcohol (CIWA-Ar) score  $> 3$  will be excluded from scanning, and those with significant alcohol withdrawal (i.e., CIWA-Ar score  $> 10$ ) will be referred for treatment at the MUSC Center for Drug and Alcohol Program's walk-in outpatient clinic. An inpatient substance detoxification unit is also available if necessary. Both units are less than a block away from the scanner and routinely accept admissions from addiction research studies. If, in the judgment of the investigator or subject, more acute treatment is necessary, the subject will be escorted to the MUSC Emergency Department, which is also less than a block away.
3. To minimize the risks of liver cell damage from study medications, we will only enroll individuals in the study who 1) report no history of past liver disease, including gastritis, pancreatitis, colitis, or peptic ulcer disease; and 2) have normal liver enzymes (ALT and AST) during screening, as determined by the CIAC assessment.

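### Liver enzymes are left off the over-one-week repeat list and the qualifying test has no age limit, so tolcapone can be started on an out-of-date normal result

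*Combined protocol and SAP*

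**What the plan says.** All references are to the combined protocol and SAP.

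- **Repeat rule (B.1).** If more than a week has gone by since the intake core's assessment, "urine drug screening and pregnancy testing will be repeated", and the recent-drinking measures are taken again. Liver enzymes are not mentioned. The examples given in that sentence belong to the drinking measures only.
- **Eligibility (Exclusion Criteria, item 10).** The bar is ALT or AST "greater than the upper limit of the normal range at screening".
- **When that test is done (C.1.a and C.2.b item 3).** "During assessment at the CIAC, subjects will receive liver function tests", and only those with normal results go on to genotyping and referral. Enrolled subjects must "have normal liver enzymes (ALT and AST) during screening, as determined by the CIAC assessment".
- **Safety rationale (B.3.a).** Only people who report no liver disease and "have normal liver enzymes prior to randomization will be enrolled in the study".
- **Day 1 (B.4.a and Table 2).** "Following the scan, blood will be collected for the red blood cell COMT activity assay"; randomization and the first dose come next. No liver test is listed for that day.
- **Next liver test (Tables 2 and 3, B.3.a, C.2.b item 4).** It is on day 7 or 8, once dosing is over. The day 4 contact asks about symptoms only.

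**The concern.** Section B.3.a recognises that heavy drinkers may be more vulnerable to liver injury, and answers this by admitting only people with normal enzymes and no liver history. That safeguard is only as good as the enzyme result is recent. The subjects average at least 20 drinks a week and are free to go on drinking between intake and day 1. The plan treats their drug screen, pregnancy test and drinking record as needing renewal after a week, but not the result that guards against tolcapone's main known hazard.

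If enzymes have risen in the meantime, no blood test shows it before exposure ends. An old baseline also makes the day 7 or 8 result harder to read, because an elevation that predated dosing could be taken for a drug effect.

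The absence of a liver test during the seven-day course is a reasoned choice in B.3.a and C.2.b, and is not in question. This point concerns only elevations already present at the first dose.

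**Working it through.** **Reading the text.** The plan gives no figure to reproduce, so the first step is to follow a subject through it.

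1. The liver test is done at intake (C.1.a). Genotyping and referral follow, so some delay is built in, and B.1 expects that it may exceed a week.
2. After a week, the drug screen, pregnancy test and drinking measures are renewed (B.1). ALT and AST are not.
3. The three statements of the liver criterion refer to screening (item 10), to before randomization (B.3.a), and to screening as assessed by the intake core (C.2.b item 3). The B.3.a wording fixes an order, not a window. An intake result of any age satisfies all three.
4. Day 1 blood is described only for the COMT assay (B.1, B.4.a).
5. The next enzymes are measured after the last dose.

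No step stops a subject whose normal value is out of date.

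**How many could be affected.** The documents do not give the intake-to-day-1 interval or a rate of change from normal to raised. What follows is a range under stated assumptions, not an estimate.

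Inputs from the documents: 90 planned, half on tolcapone (C.1.a); "over 70 who have been enrolled in the current protocol" (B.3.a), taken as 71; and "In our current ARC study, 23% of subjects had elevated liver enzymes" (B.3.a).

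*Assumption 1, subjects remaining (R):*
- all 71 randomized, none replaced: 90 − 71 = 19
- 10% not randomized or replaced: 90 − 0.9 × 71 = 26.1
- 20% not randomized or replaced: 90 − 0.8 × 71 = 33.2

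Since the text says over 70, 19 is a maximum for the first case. Half on tolcapone gives 9.5, 13.1 and 16.6.

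*Assumption 2, share with a stale and now raised value (q):* 1-10%. The 23% figure serves only as a ceiling. Using it would mean that every remaining test is stale and that an earlier normal result tells us nothing.

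Expected tolcapone starts with raised enzymes = (R ÷ 2) × q:

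| q | R = 19 | R = 33.2 |
|---|---|---|
| 1% | 9.5 × 0.01 = 0.10 | 16.6 × 0.01 = 0.17 |
| 5% | 9.5 × 0.05 = 0.48 | 16.6 × 0.05 = 0.83 |
| 10% | 9.5 × 0.10 = 0.95 | 16.6 × 0.10 = 1.7 |
| 23% (ceiling) | 9.5 × 0.23 = 2.2 | 16.6 × 0.23 = 3.8 |

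Late exclusions if the test is repeated, both arms, R = 19: 19 × 0.01 = 0.19 to 19 × 0.10 = 1.9.

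The open-label pilot (A.4) had one minimal elevation among five subjects. It arose in a study where everyone received tolcapone, and the text does not say whether it was present before dosing, so it is not used as a rate.

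**The case against.** The omission itself is hard to dispute. The case against is about weight.

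- **The intake core may already set a window.** Its procedures are not supplied. This stands as a limit: the document permits dosing on an old value, but does not show that it happens.
- **The repeated items have their own reasons for being recent.** Drug use has 30-day and 7-day exclusion windows, pregnancy is a current state, and drinking is a model covariate. So B.1 need not imply that every intake result lapses after a week. That is fair, and one week for enzymes is a convenient choice, not a derived one. But raised enzymes are also a current-state exclusion, they can change with drinking, and no reason is given for leaving them out.
- **The numbers are assumed.** True. The 1-10% range has no source in the documents, and at the low end the expected count is 0.1.
- **Harm over seven days is unlikely.** The severe cases cited in B.3.a were four in about 60,000 patients, dosed for two to four months. That section also reports no enzyme elevations in the smoker and gambler studies. Liver-history exclusion, the day 4 and day 7 symptom checks and the day 7 or 8 test add protection. This limits the likely consequence. It does not explain why a criterion meant to hold at dosing need hold only at intake.
- **Little remains to change.** B.3.a says the procedure has worked well in ten pilot subjects and over 70 here. It reports neither test-to-dose intervals nor day 1 enzyme values, so it cannot show that the gap was harmless.

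**Conclusion.** The concern holds. This document sets no age limit on the qualifying ALT and AST, leaves them off its own re-check list, and measures them next only after dosing ends. The text makes that clear. How often it matters is uncertain: about 0.1 to 1.0 tolcapone starts with raised enzymes if 19 subjects remain, or 0.2 to 1.7 if about 33 remain, assuming 1-10% have a stale and now raised value. The ceilings are 2.2 and 3.8. These are small numbers, and severe injury in seven days is unlikely, so this is a change that should be made, not one that puts the trial in doubt. If the intake core already enforces a window, the remedy is only to write it into the protocol.

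**What to change.** For subjects still to be enrolled, add ALT and AST to the over-one-week repeat list in B.1, and require that the result be checked against exclusion criterion 10 before the first dose. Because scan, blood draw, randomization and first dose share day 1, this needs a same-day result, a draw shortly before day 1, or a short delay.

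The cost is one routine assay per remaining subject seen more than a week after intake. At the assumed 1-10%, 0.2 to 1.9 of 19 subjects would be excluded late. This bites most for met/met, where B.5.b expects about 31 subjects for a target of 30. Exclusion before randomization loses no randomized data.

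A weaker fallback is to run the enzymes on the existing day 1 blood and stop medication promptly if a value is above the upper limit. By Table 3, with results by the end of day 1, a subject would have taken 2 doses (2 × 100 = 200 mg). By the end of day 2 it would be 5 doses (200 + 300 = 500 mg). That is 6.7% to 16.7% of the full 3,000 mg course (200 + 300 + 300 + 3 × 600 + 400). The turnaround is assumed, and this route can lose randomized subjects, so it is second best.
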